5.0 Study Design

5.1 Overview of Study Design: This study is a 3 arm, prospective, randomised, proof of principle clinical trial to determine the optimal treatment duration for achieving a measurable physiologic effect on lower extremity lymphoedema with the Flexitouch® system (FT) as determined by bioimpedance, perometry, tonometry, ultrasound, local tissue water assessment, symptom burden and subject interview.. Each intervention arm will include 10 completed subjects for a total of 30 completed subjects.

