6.2 Recruitment and Randomisation

6.2.1 Recruitment Plan: Subjects will be recruited from patients either seeking or who have previously sought treatment at a clinic for lymphoedema. Desired enrollment/follow-up time (first subject in to last subject out) is 20 weeks. If additional recruitment is required to meet enrollment, referring general practitioners and potential reference clinics may be solicited for subjects. Patient advocacy/support groups may also be notified of the study opportunity. Subject recruitment materials may be provided for referring physicians' waiting rooms including posters, flyers, brochures, etc. If additional recruitment is required, direct to public advertisements in local newspapers may be utilized.

6.2.2 Randomisation Scheme: After completing the informed consent, subjects will be randomly assigned equally to one of three groups. Randomisation will follow the computer generated scheme. A master copy of the scheme will be kept at TSTI.

The site(s) will be provided with sealed envelopes containing the device assignment for each potential subject. Each envelope will be numbered sequentially from 01 to 030. Randomisation envelopes and/or subject IDs cannot be used more than once. After the subject signs the informed consent agreeing to participate in the study, the appropriate study staff will obtain the next sequential sealed randomisation envelope and open it while the subject is present.

The randomisation assignment cannot be changed or chosen by the subject or the investigator. The randomisation envelope should be placed in the subject binder.

6.3 Study Timetable:

Task	25 Weeks				
	1-5	6-10	10-15	15-20	21-25
EC/Regulatory	X	X			
Enrollment		X	X	X	
Treatment		X	X	X	X
Data Entry		X	X	X	X
Data Analysis				X	X

7.0 Treatment Plan and Study Procedures:

7.1 Dosage and Rationale: All subjects enrolled will receive treatment to the study leg using the FT study device. The treatment will be received in clinic and the garments applied by a trained clinician with the exception of Group A's weekend treatment which will be done by the patient in their home.

Subjects will be randomised into one of three groups. Following randomisation and study arm assignment the subjects will receive treatment according to study arm assignment:

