- After all randomisation assignments have been assigned via the randomisation scheme. The site will review the subject withdrawal list and replace the subject according the sequence of subject withdrawal. For example: If first subject withdrawal is from Group A then the second from Group C. The next eligible subject would be enrolled in Group A followed by Group C. This will continue until there are 10 subjects completed in each study group for a total of 30 completed subjects.

10.0 Deviations from the Clinical Protocol: Any deviation from this Clinical Protocol undertaken to protect the life or physical well-being of a subject in an emergency

situation must be reported to the sponsor and the respective EC as soon as possible, but in no event later than five (5) working days after the emergency occurred. Anticipated deviations from this plan in a non-emergency situation must be pre-approved by the sponsor via telephone, e-mail, fax, or mail. It is preferred that deviations scheduled to be performed in a nonemergency situation not be conducted until written authorization via fax, mail, or e-mail is provided by the sponsor. All protocol deviations must be documented. Deviations that may affect the scientific soundness of the study, or the rights, safety or welfare of the subjects must also be reported to the reviewing EC according to their reporting requirements. Protocol deviations may necessitate the discontinuation of the subject from the study.

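### Replacement subjects enrolled after envelope 030 take the arm of the next name on the site's withdrawal list, so they are neither randomised nor concealed

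*Combined protocol and SAP*

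**What the plan says.** Section 5.1 states that "This study is a 3 arm, prospective, randomised, proof of principle clinical trial", with 10 completers per arm and 30 in all. Section 8.1 also calls the trial randomised. Section 6.2.2 says that "After completing the informed consent, subjects will be randomly assigned equally to one of three groups", and section 7.4.1 repeats this. The scheme is computer generated and the sponsor keeps the master copy. For the envelopes, "Each envelope will be numbered sequentially from 01 to 030" and "Randomisation envelopes and/or subject IDs cannot be used more than once". Staff are to "obtain the next sequential sealed randomisation envelope and open it while the subject is present".

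Section 8.2 adds that, once 30 are randomised, subjects who miss treatment visits are replaced until every group has 10 with complete data. Section 9.3 gives the method. It starts "After all randomisation assignments have been assigned via the randomisation scheme", and then: "The site will review the subject withdrawal list and replace the subject according the sequence of subject withdrawal". The worked example, with a first withdrawal from A and a second from C, is that "The next eligible subject would be enrolled in Group A followed by Group C".

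No section provides extra envelopes, a reserve list or any concealment for these subjects.

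**The concern.** A replacement's arm is fixed by a list that the site itself keeps. Because staff open each envelope, they know the arm of every subject who withdrew, and so they know the arm waiting for the next person before consent or eligibility is settled.

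Entry leaves room for judgement. The clinician decides whether swelling is clinically relevant and whether compression garments are adequate, and the subject must be able to attend every clinic visit (section 6.1.1). The visit burden differs by arm: group A has ten clinic days and a weekend at home, while groups B and C have morning and afternoon sessions on five days (sections 7.1 and 7.4.9). Staff who know the next slot could, without any ill intent, judge or time a candidate's entry to suit that schedule.

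Replacements count toward the 10 completers per arm and enter the between-arm comparisons. Section 8.2 uses the resulting effect sizes to plan the definitive study. The models in section 8.2.1 protect only in part: group and day are forced in, but the baseline value, BMI, age and the other covariates are merely candidates.

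**Working it through.** **1. Envelopes against target.** 3 arms × 10 completers = 30 (sections 5.1 and 8.2). There are 30 envelopes, 01 to 030, and none may be reused (section 6.2.2). The plan's figure reproduces and leaves no spare assignment, so any replacement must be allocated under section 9.3.

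**2. How many subjects this affects.** The documents give no drop-out rate, so I assume the same rate d in every arm.

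- Chance of at least one non-completer among the first 30: 1 − (1 − d)^30.
- Expected replacements: 30d/(1 − d). This allows for replacements who drop out in turn.
- Completers per arm who are replacements: 10d.

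| Assumed d | At least one needed | Expected replacements | Non-randomised among each arm's 10 completers |
|---|---|---|---|
| 5% | 79% | 1.6 | 0.5 |
| 10% | 96% | 3.3 | 1 |
| 20% | 99.9% | 7.5 | 2 |
| 30% | about 100% | 12.9 | 3 |

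For example, at 10%: 30 × 0.10/0.90 = 3.3. The 30% row may be pessimistic for a treatment phase of 5 to 12 days.

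**3. What it could do to an estimate.** The documents give no basis for a size of bias, so this is an illustration only. Suppose that every replacement in one arm differed from the randomised subjects by 1 SD in the same direction. The mean of that arm's 10 completers would shift by d × 1 SD: 0.05, 0.1, 0.2 or 0.3 SD. The standard error of a difference between two arms of 10 is sqrt(1/10 + 1/10) = 0.447 SD. The shift is therefore 0.11, 0.22, 0.45 or 0.67 standard errors.

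**4. How predictable the next arm is.**

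| Rule | Correct guesses of the next arm |
|---|---|
| Section 9.3 as written | 100% |
| Route 1: list extended in undisclosed blocks of 3 and 6; site guesses the arm least used so far | about 50–55% |
| Route 2: vacant slots released in random order; site guesses the arm with most vacancies; d = 5%, 10%, 20%, 30% | about 82%, 74%, 64%, 59% |

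The last two rows come from simulation. Route 2 stays guessable because often only one arm is vacant: for about 62%, 42%, 24% or 16% of replacements at the four rates, the next arm is certain even so.

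**The case against.** - **Section 9.3 is explicit and section 8.2 announces replacement, so nothing is contradicted.** It is fair that a specific rule may qualify a general label. But stating a rule does not make it random or concealed, and sections 5.1, 6.2.2, 7.4.1 and 8.1 never say that replacements are not randomised.
- **The effect is small and the trial is an unpowered pilot.** At 5–10% drop-out this stands: even with every replacement in an arm 1 SD off in the same direction, the shift is 0.11–0.22 standard errors. Pilot status excuses low power. It does not excuse an avoidable source of bias in the effect sizes the pilot exists to produce.
- **There is no obvious motive.** All arms receive the same active device, and the documents point to no direction of steering. This limits what may be claimed, but differing schedules could still influence who is enrolled into which slot.
- **Originally randomised subjects stay in the analysis.** Sections 6.1.3, 8.2 and 9.3 keep withdrawn subjects' data in the intention-to-treat analysis. This softens the problem but does not randomise those who replace them.

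A reader might also infer more than the documents support:

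- **That the trial as a whole is not randomised.** The first 30 allocations are unaffected, and if nobody withdraws the rule is never used.
- **That staff choose the arm.** They do not; the list order fixes it. They can influence only who is enrolled next, and when.
- **That non-randomised subjects will pile up in one particular arm.** The documents give no drop-out rates by arm. Assuming that risk follows treatment days points to A, and assuming that it follows treatment hours points to C, so neither can be asserted.
- **That predictability should be judged against a one-in-three guess.** Neither remedy reaches 33% in an open trial.

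**Conclusion.** The point holds and should be fixed. Under section 9.3 every subject enrolled after envelope 030 is allocated without a random step or concealment, and the site can know the next arm with certainty. That conclusion rests on the text alone. Its extent depends on assumed drop-out: 5–30% of each arm's completers at an equal 5–30%. Steering is possible, not shown, and no size of bias is claimed. The illustration in standard errors assumes a 1 SD difference that the documents neither state nor suggest. It becomes appreciable only toward the upper end of the range.

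**What to change.** Replace the withdrawal-order rule in section 9.3 with allocation held by the sponsor, by one of two routes.

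1. **Extend the list (preferred).** Add computer-generated assignments beyond 030 in further sealed, sequential envelopes, using undisclosed blocks of varying size (for example 3 and 6). Treat 10 completers per arm as a target. State that subjects already randomised when the 30th completes will finish and be analysed. Align sections 5.1, 8.2 and 9.3, including the stated maximum of 30 completers.
2. **Release vacant slots at random.** If exactly 10 per arm must be kept, the sponsor holds the vacant slots and releases them in concealed random order.

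Under either route, identify the replacements in the report. Where replacements are still tied to vacated slots (route 2, or section 9.3 left unchanged), add a sensitivity analysis of all subjects randomised from envelopes 01–30, including the partial data of those who withdrew.

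**Cost.** Both routes need protocol wording. Route 1 needs on average 32, 33, 37 or 43 envelopes in total at 5%, 10%, 20% or 30% drop-out. It gives up exact balance: with equal drop-out the smallest and largest arms average about 9 and 11 completers, for a standard error of sqrt(1/9 + 1/11) = 0.449 SD against 0.447 SD. Arms would be more uneven if drop-out differed strongly between them, and the total may slightly overshoot 30. Route 2 keeps 10 per arm but remains the more guessable of the two.

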12.0 General Study Information

12.1 Technical Support: Training and support for study procedures will be provided by the Sponsor contact listed in Section 1.1 or designee.

12.2 Discontinuation of the Study: The study may be terminated if:

- That the rate of severe adverse events in any arm of the study is such that the Ethics Committee decides continued participation would compromise subject safety. If deemed necessary by the Ethics Committee, a follow-up safety analysis will be performed for all subjects.
- Target subject accrual has not met, and cannot meet subsequent trial objectives.

Upon study termination by Sponsor, Sponsor will compensate Institutions for actual Study costs incurred through the close out of the Study, in accordance with the terms of the study contract.

12.3 Record Retention: Records must be maintained for a period of at least ten years after the date on which the study is completed or terminated. Investigator or Institution shall notify Sponsor at least thirty (30) days prior to any planned archiving or destruction of records related to this study. The recordings from the patient interviews will be transcribed and the recording then deleted. The transcription will be maintained with the study records.

12.4 Quality Assurance Procedures: This study will be conducted in accordance with Good Clinical Practice and International Conference on Harmonization Guidelines, NHS Trusts, institutional research policies and procedures and other appropriate regulatory requirements to ensure subject safety and quality of clinical procedures related to the conduct of the clinical trial. The investigators will permit regular monitoring, audits and site inspections by the EC, the sponsor, government regulatory bodies and any institution compliance and quality assurance groups of all study related documents (e.g. source documents, regulatory documents, data collection instruments, study data, etc.). The investigator will ensure the capability for inspection of applicable study related facilities. Regular trial monitoring will be conducted to ensure compliance to this protocol.

12.5 Materials Provided by the Sponsor: Sponsor will provide administrative study materials along with the FT controllers and garments, PicoPress® and pedometers.

12.6 Materials Provided by the Site: Institution will provide assessment equipment (scales, lab tests, perometer, bio impedance equipment, tonometer, clinical and support staff) needed to complete the trial.

13.0 Administrative Study Information

13.1 Pre-Study Site Visit: The study sponsor may conduct onsite visits or telephone qualification (pre-study audit) prior to study initiation to ensure to verify adequate resources, staffing and a sufficient subject pool.

13.2 Ethics Committee Review: Prior to subject enrollment and study initiation, the appropriate Ethics Committee and National Competent Authority (if applicable) must approve the clinical study. It is the responsibility of the investigator to provide the Ethics Committee with all necessary information to satisfy the individual institution's requirements.

13.3 Clinical Site Monitoring: Clinical sites will be monitored for compliance with the clinical protocol, investigator agreement, and applicable regulatory regulations. Regular contact will be maintained to ensure:

- Subject safety,

- That clinical site staff is well informed of regulations and sponsor requirements,
- That the clinical protocol is followed,
- That data is gathered in a complete and timely way,
- That problems with data or data collection are addressed appropriately and in a timely manner,
- That adverse events are properly reported in a timely manner.
- Investigator and Institution will permit trial related monitoring, audits, EC review, and regulatory inspection(s), providing direct access to source data and documents as legally appropriate. Monitoring will be performed by study sponsor and/or local study monitor. Monitoring will review subject source documentation and Case Report Forms for accuracy, completeness, and compliance with Good Clinical Practice procedures. Monitoring site visits will be performed at approximately quarterly intervals. Additional site visits may be scheduled at the discretion of the Sponsor upon review of the monitoring reports. In addition to site visits, a screening log will be submitted to Sponsor or designee by the sites as requested (by fax or e-mail). This screening log will be reviewed with the site for plan vs. actual recruitment purposes.

13.4 Investigator Records and Reports: Records to be maintained by the investigator in a designated study file include:

- Investigational plan and all amendments
- Signed Investigator Agreement
- EC approval letter, including a copy of the approved consent forms, progress reports, Adverse Event Report
- EC roster or Assurance number, if applicable
- All correspondences relating to the conduct of this study between the site and sponsor, ECs, and study monitor
- Curriculum Vitae and professional license for all study personnel, if applicable
- Site personnel signature and documentation regarding the Investigator's delegation of responsibility
- Clinical Site Visit log
- Protocol/device related training records for all applicable study personnel
- Investigational device inventory information including the date, quantity and serial number of all devices and received identification of all subjects who received treatment, and final disposition of the devices.
- Screening log
- Financial Disclosure documentation for the Investigator and Co-Investigators, if applicable
- Reports (see Table 1)

The following records must be maintained for each subject enrolled:

- Signed and dated informed consent forms
- Completed CRFs, queries and source document worksheets (if applicable)
- Complete medical records including procedure reports, lab reports (if applicable), etc.
- Records pertaining to a subject's death during the investigation

Investigators are required to prepare and submit to the sponsor or its designees complete accurate and timely reports on this investigation as required by regulations. The types of reports to be submitted are summarized in Table 1.

Table 1: Investigator Reports

Reports	Submit To	Timeframe
Unanticipated Adverse Device Event	Sponsor and Reviewing EC	As soon as possible but no later than 10 working days
Withdrawal of EC Approval	Sponsor	Within 5 working days
Progress	Sponsor, Monitor and Reviewing EC	Annually, at a minimum
Final	Sponsor and Reviewing EC	Within 3 months following the completion or termination of the Investigator's part

Subject study records, correspondence files, all supporting study documentation, and reports must remain on file at the investigational site for a minimum of ten years after the conclusion of this study or when it is no longer needed to support a marketing application, whichever is later. All investigators must contact Tactile Systems prior to destroying or archiving off-site any records and reports pertaining to this study to ensure that they no longer need to be retained on-site.

Additionally, Tactile Systems must be contacted if the Investigator plans to leave the investigational site to ensure that arrangements for a new Investigator or records transfer are made prior to the Investigator's departure.

13.5 Changes Necessary After Study Initiation: Should changes in the study plan or protocol become necessary in the course of the clinical trial, those specific changes will be discussed and agreed upon by the Sponsor, its acting representative if appropriate, Investigator, and appropriate EC

approval obtained before the changes are implemented. All changes must be documented.

15.0 Appendices
